## **7. Clinical Ethics and Clinical Trial Registration**

The study follows the “Helsinki Declaration” and other relevant regulations, the clinical study was carried out after approved by the Central Ethics Committee. Before each subject was enrolled in the study, it was the investigator's responsibility to provide the subject or his agent with a complete and comprehensive introduction of the purpose, procedure, and potential risks of the study, and to sign an informed consent form so that the subject knowing that they have the right to withdraw from this study at any time, informed consent should be retained as a clinical research document. Before collecting the first case, the central ethics approval was completed and the clinical trial registration was completed.

## **Analysis methods**

### **1. Sample size estimation**

Sample size estimation was by using PASS(version 11.0) software. According to document analysis and trial test, the WOMAC joint function scores could change by  $13.0 \pm 5.6$  after treatment of positive drug control group.(Qilin Liu. Observation on clinical effect of KOA by needling with moxibustion[J]. TCM clinic Research,2016,8(09):108-109.), while needling group changed by  $8.8 \pm 3.7$ (Acupuncture for Chronic Knee Pain A Randomized Clinical Trial), EA group changed by  $8.9 \pm 4.0$ (trial test), Moxibustion group changed by  $10 \pm 4.7$ (trial test), Warm needling group changed by  $12.0 \pm 6.1$ (Jianbo Wang, Yanlin Wang, Yongqi Lu, Yaochi Wu. Effect analysis of KOA by needling with moxibustion[J]. Shanghai acupuncture magazine,2010,29(06):390-392.), Sham acupuncture group changed by  $5.8 \pm 3.0$ (Acupuncture for Chronic Knee Pain A Randomized Clinical Trial). In the condition of  $\alpha=0.05$ , the power of test was  $1-\beta=0.9$  and the six groups were distributed according to 1:1:1:1:1:1 ratio, and the sample amount is at least 42. The sample size is to be expanded by estimated 20% dropout rate, and finally, there are at least 53

---

patients in each group. In view of the equality of the distribution of all cases in six centers, there were a total of 360 cases with 60 patients in each group. The following equation was used:

$$n = \psi^2 \left[ \sum_{i=1}^k s_i^2 / k \right] / \left[ \sum_{i=1}^k (\bar{X}_i - \bar{X})^2 / (k-1) \right]$$

## 2. Random allocation

The block randomization is operated by the central randomization system (by telephone and online). When the subjects met inclusion exclusion criteria of the study, The randomization of the central random system is conducted by assigned personnel or clinical investigators of each center. The randomization scheme of this study is produced by the Clinical Evaluation and Analysis Center of Zhejiang Provincial Hospital of TCM which is not involved in the statistical analysis of this project . The randomization scheme of this study and The parameters set during the process of the program are called the bottom of the blind, which is generated by the random scheme personnel to sign and seal, and taken care of by the specialized personnel not involved in the project of the Clinical Evaluation and Analysis Center of Zhejiang Provincial Hospital of TCM. The central random system has strict personnel authority, and other than the highest level system management staff, no one has access to the random scheme in the central random system.

## 3. Design and implementation of blind method

The blind(patient-blind) design is adopted in this program, and the patients are evaluated by blind method. Index evaluation and data recording, treatment operator and statistician are all separated. The random member and the therapist know the grouping; The curative evaluators and the statisticians were not aware of the grouping.

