## **The Study Protocol of the project**

### **Different kinds of acupuncture treatments for Knee Osteoarthritis: a Multi-center Randomized controlled trial**

#### **Research objectives**

(1)The study aims to exam different kinds of acupuncture treatment for treating knee osteoarthritis (KOA), compared with the effective drug control group respectively, and confirm the efficacy of different acupuncture treatments of KOA, and further a safe, effective and easily-spread therapy for KOA.

(2)To observe and compare the effects between groups of different acupuncture treatment: acupuncture group, moxibustion group and warm-needling group, and make clear whether the moxibustion play a key role in the acupuncture treatment for KOA.

(3) To compare the effects of acupuncture group and sham-needle group and make clear whether acupuncture is effective in KOA treatment.

(4) To compare the effects of electro-acupuncture group and the warm-needling group, to explore whether there are different clinical effects of electric stimulation and warm stimulation in acupuncture treatment of KOA.

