## 4. Interventions

The six groups of participants (except for western medicine group) will be treated with different kinds of acupuncture treatment. **The unified needle** is the single-use, sterile steel, size 0.30×25mm or 0.30×40mm needle(Huatuo brand disposable acupuncture needle, Suzhou Medical Co., Jiangsu, China),it will be used in Ordinary acupuncture group,

---

electro-acupuncture group and Warm-needling acupuncture group; **The unified moxa** is the 2cm Yufu brand Qing Ai(Jiangsu Kangmei Pharmaceutical Co. Ltd. Jiangsu, China,Z32020253 ),it will be used in Mild moxibustion group and Warm-needling acupuncture group; **The unified Electro-acupuncture apparatuses** is the Huatuo SDZ-IIB electro-acupuncture apparatus(Jiangsu Suzhou Medical Supplies Factory LTD. Jiangsu China ),it will be used in electro-acupuncture group; **The unified Leather measuring tape** is: Type 8214 ,Size 1.5m\*7.5mm produced by Deli Group Limited; **The unified acupuncture time and therapy course** were: Each treatment lasts for 30 minutes which will be applied 3 times a week(ideally every 1 or 2 days ) for consecutive 4 weeks, 12 sessions in total; **Operator and attention:** Acupuncture treatments will be operated by the attending doctor and should pay attention to the disinfection of operator's hands and local skin before and after treatment. The treatment of acupuncture and moxibustion will be mainly aimed at the knee joint with pain symptoms, such as single or bilateral knee pain, the treatment of single / bilateral knee joint. **The unified emergency medication and treatment:** If the participants have unbearably knee pain during the study, we will allow them to take temporary emergency medication: oral Celebrex capsules (Celebrex, Capsules, Pfizer Pharmaceuticals Ltd), which will be applied once a day (0.2g a time orally).The situation of drug use should be recorded in detail; swelling of the knee joint during the test and temporary receiving treatment, but it should be recorded in detail. swelling in the knee joint effusion shown during test, allowed to accept fluid pumping treatment, but it should also be recorded in detail.

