#### **(6)Celebrex group**

Celebrex capsules (Celebrex, Capsules, Pfizer Pharmaceuticals Ltd), which will be applied 1 time daily( 1 time oral 0.2g) for 4 weeks.

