#### **(1) Primary outcomes**

1)Visual Analogue Scale (VAS);

2)WOMAC function score;

The primary outcome measurements will take the average of the last three days.

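### The plan claims a patient-blind design for the whole trial, but at most one of the nine contrasts implied by the objectives can be masked to the patient

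*Combined protocol and SAP*

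**What the plan says.** The section on the blind method states: "The blind(patient-blind) design is adopted in this program, and the patients are evaluated by blind method". No arm or comparison is excepted. The same section says "The random member and the therapist know the grouping" and "The curative evaluators and the statisticians were not aware of the grouping".

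The Interventions section says "The six groups of participants (except for western medicine group) will be treated with different kinds of acupuncture treatment". The drug arm receives "Celebrex capsules (Celebrex, Capsules, Pfizer Pharmaceuticals Ltd), which will be applied 1 time daily", and no needling is described for it.

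Objective 1 has the acupuncture treatments "compared with the effective drug control group respectively" and aims to confirm their efficacy. Objective 2 compares "acupuncture group, moxibustion group and warm-needling group". Objective 3 compares acupuncture with sham needling, and objective 4 compares electro-acupuncture with warm needling.

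The primary outcomes are VAS and WOMAC function. On their timing the plan says "The primary outcome measurements will take the average of the last three days".

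**The concern.** A patient knows whether he or she swallows a capsule, feels a current, has moxa burning at the knee or has needles alone. The plan describes nothing that would disguise these differences, so the design lacks a property that the plan states for it.

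This matters because of how the primary outcomes arise. VAS and WOMAC function depend on what the patient reports. If a patient knows the treatment and holds a view about it, that view can enter the score before any evaluator sees it. Evaluator masking protects a measurement taken by the evaluator, such as knee swelling, but that outcome is secondary.

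At stake is the reading of the drug and modality comparisons. Under an unqualified patient-blind label, a reader would take them as protected from patient expectation when they are not. Objective 1, which seeks to confirm efficacy against the drug, is the most exposed.

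**Working it through.** The plan gives no figure for blinding, so there is none to reproduce. The check is a count of contrasts, set against what the patient sees and feels in each arm.

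**Step 1. Arms as described (Interventions, items 1 to 6).**

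| Arm | What the patient experiences |
|---|---|
| Acupuncture | 0.30 mm needles at six points, manipulated to De Qi |
| Electro-acupuncture | the same needling, plus current through two of the points, set within tolerance and preferably with slight visible twitching |
| Mild moxibustion | needles at four points; moxa burned 2-3 cm from the skin at the other two |
| Warm needling | needles at all six points; moxa burned on the needles at two of them |
| Sham | 0.18 mm needles, 1-2 mm deep, 1 cm lateral to the points; five points listed; no manipulation described |
| Celebrex | a capsule once daily for 4 weeks |

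**Step 2. Contrasts implied by the objectives.**

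| Objective | Contrasts | Number | What gives the treatment away |
|---|---|---|---|
| 1 | acupuncture, electro-acupuncture, moxibustion and warm needling, each against drug | 4 | procedure at the knee against capsule |
| 2 | acupuncture against moxibustion; acupuncture against warm needling | 2 | moxa against none |
| 2 | moxibustion against warm needling | 1 | moxa above the skin against moxa on inserted needles |
| 3 | acupuncture against sham | 1 | nothing certain: needles only in both |
| 4 | electro-acupuncture against warm needling | 1 | current against burning moxa |

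Total: 4 + 3 + 1 + 1 = 9. Open to the patient as described: 4 + 3 + 1 = 8. Possibly masked: 9 - 8 = 1.

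**Step 3. Sensitivity of the count.** If objective 2 is read as a single three-group comparison, the total is 4 + 1 + 1 + 1 = 7 and at most 1 of 7 is masked. The conclusion does not depend on the reading.

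**Step 4. Why at most one.** Sham and real acupuncture differ in gauge (0.18 against 0.30 mm), depth (1-2 mm against 0.5 to 2.0 cun, depending on the point), manipulation (none described against De Qi) and points listed (five against six). The exclusion criteria rule out acupuncture only in the past month, so patients with earlier experience may enrol and may recognise shallow needling. Masking is attempted there; the documents do not show that it holds.

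**Step 5. Direction.** The sample size section assumes a WOMAC function change of 13.0 on drug and 8.8, 8.9, 10 and 12.0 on acupuncture, electro-acupuncture, moxibustion and warm needling. The assumed gaps are 13.0 - 8.8 = 4.2, 13.0 - 8.9 = 4.1, 13.0 - 10 = 3.0 and 13.0 - 12.0 = 1.0, all in favour of the drug. Expectation favouring acupuncture would narrow them and expectation favouring the drug would widen them. The documents do not say which to expect.

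**The case against.** The strongest reply is that this is loose wording rather than a flawed design. The text reads as a rough translation. The sentence that lists who is unaware of the grouping names evaluators and statisticians, not patients, and evaluation of patients by a blind method may simply mean masked assessment. Part of this stands: the intent may have been narrower than the words. But the parenthesis says patient-blind without limit, and it needs correcting on any reading.

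Second, recognising a procedure is not the same as expecting more from it. This also stands. Moxibustion and warm needling both use needles and moxa, and electro-acupuncture and warm needling are both active treatments; the documents show no expectation gradient within either pair. The eight open contrasts are therefore not equally vulnerable.

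Third, the plan does not state how the scales are administered, and averaging over three days does not itself show self-report. That is fair, but pain on a VAS and WOMAC function are patient ratings whoever records them. The consent pages are not available for review, so what patients were told is unknown.

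Two stronger readings are tempting and are not supported:

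- A reader might size the bias from the assumed sham change, since 5.8 / 8.8 = 66% of the acupuncture change. That change may also contain natural course and regression to the mean, given entry at a VAS of 4 or more. Nothing in the documents says what share is expectation or how it differs by arm.
- A reader might infer that the plan claims to control expectation effects. It makes a statement about blinding and says nothing about expectation.

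**Conclusion.** The concern holds as an error in the stated design. The patient-blind claim is wrong as written for eight of the nine contrasts implied by the objectives, and unproven for the ninth. It is strongest for the four drug contrasts and weakest for moxibustion versus warm needling. Masked evaluators do not cure it, because both primary outcomes rest on the patient's rating.

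The conclusion rests on three things: the objectives read as pairwise contrasts, the arms taken as described with no undisclosed dummy procedure, and VAS and WOMAC function taken as patient-rated. It does not rest on any estimate of bias, whose size and direction cannot be had from these documents. Nor does it follow that the trial would produce a false claim for acupuncture: on the plan's own assumptions the drug does better than every active arm, and the effect of expectation could run either way. Randomisation is unaffected. What has to change is the description and the interpretation that follows from it.

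**What to change.** 1. In the section on the blind method, replace the claim with: *Patient masking is attempted only between the acupuncture and sham groups. All other contrasts are open to the patient, with outcome evaluators and statisticians masked.*
2. In the analysis section, state that the drug and modality contrasts will be reported as open comparisons. Any claim of efficacy beyond expectation rests only on acupuncture versus sham, qualified by how well masking held.
3. Optionally, add one guess-the-group question in the acupuncture and sham arms at an existing visit and report a blinding index. Week 2 is preferable, because a guess at week 4 is more confounded with perceived benefit. If that visit has passed, items 1 and 2 can still be made.

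The cost is an edit to the protocol and SAP, one added question if item 3 is taken up, and a weaker stated claim for the drug and modality contrasts. No new arm, dummy procedure or extra visit is needed.

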## 4. Interventions

The six groups of participants (except for western medicine group) will be treated with different kinds of acupuncture treatment. **The unified needle** is the single-use, sterile steel, size 0.30×25mm or 0.30×40mm needle(Huatuo brand disposable acupuncture needle, Suzhou Medical Co., Jiangsu, China),it will be used in Ordinary acupuncture group,

---

electro-acupuncture group and Warm-needling acupuncture group; **The unified moxa** is the 2cm Yufu brand Qing Ai(Jiangsu Kangmei Pharmaceutical Co. Ltd. Jiangsu, China,Z32020253 ),it will be used in Mild moxibustion group and Warm-needling acupuncture group; **The unified Electro-acupuncture apparatuses** is the Huatuo SDZ-IIB electro-acupuncture apparatus(Jiangsu Suzhou Medical Supplies Factory LTD. Jiangsu China ),it will be used in electro-acupuncture group; **The unified Leather measuring tape** is: Type 8214 ,Size 1.5m\*7.5mm produced by Deli Group Limited; **The unified acupuncture time and therapy course** were: Each treatment lasts for 30 minutes which will be applied 3 times a week(ideally every 1 or 2 days ) for consecutive 4 weeks, 12 sessions in total; **Operator and attention:** Acupuncture treatments will be operated by the attending doctor and should pay attention to the disinfection of operator's hands and local skin before and after treatment. The treatment of acupuncture and moxibustion will be mainly aimed at the knee joint with pain symptoms, such as single or bilateral knee pain, the treatment of single / bilateral knee joint. **The unified emergency medication and treatment:** If the participants have unbearably knee pain during the study, we will allow them to take temporary emergency medication: oral Celebrex capsules (Celebrex, Capsules, Pfizer Pharmaceuticals Ltd), which will be applied once a day (0.2g a time orally).The situation of drug use should be recorded in detail; swelling of the knee joint during the test and temporary receiving treatment, but it should be recorded in detail. swelling in the knee joint effusion shown during test, allowed to accept fluid pumping treatment, but it should also be recorded in detail.

### **(1)Acupuncture group**

1)Acupoints: Liangqiu(ST34),Xuehai(SP10),Neixiyan (EX-LE4 ),Dubi (ST35),Yanglingquan (GB 34)and Yinlingquan (SP9)

2)Point location: According to the National Standard of The People's Republic of China, the Name and Location of Acupoints, issued in 2006 (GB/T 12346-2006).

3) Location and operation of acupoints

Liangqiu (ST34) is located in the anterior femoral region, the medial end of the patellar base was 2 cun and the medial femoral muscle was raised. Operation:

---

straight 1.0-1.5 cun.

Xuehai (SP10) is located in the anterior femoral region, 2 cun of the patellar base, the lateral femoral muscle and the tendon of the rectus femoris. Operation: straight 1.0-1.5 cun.

Neixiyan (EX-LE4) is located in the center of the depression of the patellar ligament of the knee . Operation: Once outside and within the frontal plane at an angle of 45 degrees inclined 0.5-1 cun.

Dubi (ST35) is located in a depression lateral to the patellar ligament. Operation: At 90 degrees, the backward inclined 1-1.5 cun.

Yanglingquan (GB 34) is located in the depression anterior and inferior to the head of the fibula.Operation: straight 1.0-1.5 cun.

Yinlingquan (SP9) is located in the depression between the lower border of the medial condyle of the tibia and the medial border of the tibia. Operation: straight 1.0-2.0 cun.

In the Acupuncture group, the inserted needles will be manipulated using techniques including lifting, thrusting, twisting, and rotating to reach De Qi (A composite of sensations including soreness, numbness, distention, heaviness and other sensations).The treatment lasts for 30 minutes.

### **(2)Electro-acupuncture group**

Acupoints, location and acupuncture operation are the same to the above acupuncture group.

Operation: The electrode will be connected in Neixiyan (EX-LE4) and Dubi (ST35) and electrode wire will be connected to the Huatuo SDZ-IIB electro-acupuncture apparatus(Jiangsu Suzhou Medical Supplies Factory LTD. Jiangsu China ), dilatational wave with a frequency of 2/100 Hz, the current strength in participants within their tolerance (preferably with the skin around the acupoints shivering mildly without pain), for 30 minutes.

### **(3)Mild moxibustion group**

Operation: In this group, Liangqiu (ST34) ,Xuehai (SP10) ,Yanglingquan (GB 34) and Yinlingquan (SP9) are needled the same to the acupuncture group. At the same time ,mild

---

moxibustion are applied at the distance of 2-3 cm away from the skin of both the Neixiyan (EX-LE4) and Dubi (ST35) by 2 two Zhuang for 30 minutes.

#### **(4)Warm-needling group**

Acupoints, location, and acupuncture are the same to the acupuncture group.

Operation: Warm-needling are applied at both Neixiyan (EX-LE4) and Dubi (ST35). That is to insert one zhuang(about 2cm)of Qing Ai on the top of the needle, and burn the moxa at the lower end ,each acupoint applied 2 Zhuang. In the process of moxibustion, if the participants feel unbearable hot , we should be put some paper between the skin and moxa to prevent burns.

#### **(5)Sham acupuncture group**

The sham Acupoints: Sham Liangqiu(ST34), Sham Xuehai(SP10), Sham Neixiyan(EX-LE4), Sham Yanglingquan (GB 34), Sham Yinlingquan (SP9)

Positioning and operation: Sham acupuncture group choose a non-meridian and non-acupoint needling method, respectively needle 1cm lateral to the above acupoints with a 0.18 \* 25mm disposable needle with depth of 1-2mm for 30 minutes.

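### The sham arm lists five needling sites and omits a counterpart to Dubi (ST35), while the acupuncture arm needles six, so the objective 3 contrast also differs by one needle per knee per session.

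*Combined protocol and SAP*

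**What the plan says.** Under 4. Interventions, (1) Acupuncture group, the points are "Liangqiu(ST34),Xuehai(SP10),Neixiyan (EX-LE4 ),Dubi (ST35),Yanglingquan (GB 34)and Yinlingquan (SP9". That is six points, and each has its own location and needling instruction, Dubi included.

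Under (5) Sham acupuncture group, the list is "The sham Acupoints: Sham Liangqiu(ST34), Sham Xuehai(SP10), Sham Neixiyan(EX-LE4), Sham Yanglingquan (GB 34), Sham Yinlingquan (SP9". That is five points. The operating instruction is to "respectively needle 1cm lateral to the above acupoints", using a finer needle (0.18 mm against 0.30 mm) to a depth of 1-2 mm for 30 minutes.

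The other needling and moxibustion arms all treat Dubi:

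- Electro-acupuncture: "Acupoints, location and acupuncture operation are the same to the above acupuncture group".
- Mild moxibustion: four points are needled, and "moxibustion are applied at the distance of 2-3 cm away from the skin of both the Neixiyan (EX-LE4) and Dubi (ST35" covers the other two.
- Warm needling: "Acupoints, location, and acupuncture are the same to the acupuncture group".

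The general paragraph of 4. Interventions sets the course as "for consecutive 4 weeks, 12 sessions in total" and lets the number of knees treated follow the symptoms ("the treatment of single / bilateral knee joint"). Research objective (3) is the direct comparison of acupuncture with sham, intended to establish whether acupuncture is effective in knee osteoarthritis.

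**The concern.** A sham control is most informative when it differs from the real procedure only in the features the investigators meant to vary. Here those are the site (1 cm off the point), the needle gauge, the depth, and the manipulation to obtain De Qi, which is described only for real acupuncture. Needle number is not presented as one of them, yet the sham list is one site short.

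The difference would apply to every sham patient treated according to the text. It is therefore wholly aligned with treatment assignment, and no covariate adjustment or sensitivity analysis can separate it from the effect of real against sham needling. It can only be prevented or disclosed.

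The comparison of needle-related adverse events is also touched slightly. Events such as needle pain and hematoma are recorded after each treatment, and the sham arm would have fewer insertions at which they could occur.

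**Working it through.** The plan states no figure for needle number, so there is none to reproduce. The check is a count of the listed points followed by simple multiplication.

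**Inputs**

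- Acupuncture points: ST34, SP10, EX-LE4, ST35, GB34, SP9 (section (1)).
- Sham points: ST34, SP10, EX-LE4, GB34, SP9 (section (5)).
- Sessions: 12 (general paragraph of 4. Interventions).
- Knees treated: one or both (same paragraph).
- Assumption: one needle per listed point.

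**Step 1: compare the lists.** The sham list gives the acupuncture names in the same order with one dropped. The only missing point is ST35.

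**Step 2: points treated per knee, by arm**

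| Arm | Needled | Moxa without needle | Points treated | ST35 covered? |
|---|---|---|---|---|
| Acupuncture | 6 | 0 | 6 | yes |
| Electro-acupuncture | 6 | 0 | 6 | yes |
| Mild moxibustion | 4 | 2 | 6 | yes (moxa) |
| Warm needling | 6 | 0 | 6 | yes |
| Sham | 5 | 0 | 5 | no |

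Sham is the only one of these arms with nothing at, or paired to, ST35. EX-LE4 and ST35 are also the two points the plan singles out for the electrodes, the mild moxibustion and the warm needling.

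**Step 3: insertions over the course** = points × sessions × knees.

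- One knee: acupuncture 6 × 12 × 1 = 72; sham 5 × 12 × 1 = 60; difference 12.
- Both knees: acupuncture 6 × 12 × 2 = 144; sham 5 × 12 × 2 = 120; difference 24.
- Relative shortfall in either case: 12/72 = 24/144 = 1/6, about 17%.

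**Step 4: what stays equal.** Session length (30 minutes) and number of sessions (12) are the same in both arms.

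**Step 5: after adding a sham Dubi.** 6 × 12 = 72 against 72 per knee; difference 0.

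Nothing in the documents relates needle number to WOMAC or VAS, so the count cannot be turned into outcome points. Sample size and power are unaffected.

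**The case against.** The strongest reply is that this is a one-word inconsistency with no demonstrated effect on inference. The plan never says that needle number is to be matched. It does not hold it constant elsewhere either, since the mild moxibustion arm has only four needles per knee. Sham already differs by design in site, depth, gauge and De Qi, and one superficial insertion fewer per session is minor beside those. Objective 3 compares two treatment packages and does not try to isolate one component. If the omission is a slip, operators may have needled six sites anyway. The sham instruction could also be read as pointing back to the real acupuncture list, because sham sites are by definition not acupoints.

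Part of this stands. The effect on outcome may well be near zero, no rule on matching needle number is stated, and the mismatch arises only where operators follow the five-site list. High confidence belongs to the count, not to any consequence.

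The rest does not remove the point. The sham list stands directly above the needling instruction and is its natural referent; reading the instruction back four subsections is strained. If the phrase is ambiguous, six hospitals could resolve it differently, which is a further reason to correct it. The moxibustion arm has fewer needles, but it still treats ST35. The designed differences are described in the plan; this one is neither stated nor justified.

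**Conclusion.** The concern holds. As written, the sham arm receives five needles per knee per session and the acupuncture arm six, with no counterpart to ST35 and no explanation. Assuming one needle per point and all 12 sessions delivered, the shortfall per sham patient is 12 insertions (one knee) to 24 (both knees), or 17%. It is probably a drafting slip, but it sits in the operative intervention text for the arm that defines objective 3, and no analysis can undo it afterwards. Practical impact is low: no shift in WOMAC or VAS is claimed, and power, sample size and analysis sets are untouched. It should be corrected because it is clear, avoidable and very cheap to remove.

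**What to change.** Add Sham Dubi (ST35) to the list in (5) Sham acupuncture group, so that each real point has one paired sham site and both arms have six needles per knee. State in the same place that the sham sites correspond one to one with the six points of the acupuncture group, and remind operators at all six hospitals.

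If patients have already been treated, establish which list was used, report needles inserted per session by arm, and disclose any difference when interpreting objective 3.

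The cost is one added name, an operator reminder, and one more 1-2 mm needle per knee per session for sham patients. It needs no extra visits, session time or participants.
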